### 5.1 Study Schedule

The following table summarizes the intervals and data collection procedures.

**Table 1: Schedule of Events**

Study Tasks	Pre-screening	Enrollment	Execution		Follow up
	No visit	Visit 1	Prior to Procedure	Procedure Visits 2 & 3	Phone call
Eligibility Assessments					
Online or phone call pre-screening survey	x				
Informed Consent 		x			
Demographics		x			
Medical History		x			
Physical Exam		x			
Pulmonary function test		x			
Single 12-lead ECG		x			
Urine sample for the presence of cotinine		x	x		
Urine pregnancy test (Female)		x	x		
Complete blood count			x		
Inclusion/exclusion assessment		x	x		
Vital monitoring		x	x	x	
Concomitant Medication		x	x		
Urine drug screen and alcohol breathalyzer			x		
Safety Monitoring				x	
Sensors application				x	
Propofol or Propofol with Remifentanyl administration				x	
MOAA/S assessment				x	
NCM Sub-Study 				x	
Safety Assessments and Compensation					
Adverse Event Assessment 		x	x	x	x
Device Deficiency 				x	
Participant stipend 		x		x	

 Written informed consent must be obtained prior to any study-specific evaluations; for more details, refer to *CIP Section 9.2*.

 For NCM Sub-Study, refer to *CIP Appendix B*.

[figure not shown]
 All Adverse Events, regardless of relatedness or outcome, will be collected and reported; for more details, refer to *CIP Section 11*.

 Device Deficiency will be collected and reported; for more details, refer to *CIP Section 11*.

 For more details regarding the subject compensation, refer to *CIP Section 15.6*.

After successful completion of the pre-screening, qualified subjects will be invited to attend Visit 1 to complete the ICF. The Investigator or designee will inform the prospective subjects on the study procedures and explain the consenting process. Once ICF is signed, visit 1 Assessments will be performed.

At the study procedure, the volunteers will receive two regimens of anesthesia with different drug combinations, with at least a 1-week washout period between regimens. Once the pre-procedure part completed, the subject will be sequentially assigned to start with either Propofol (P) or Propofol with 4 ng/ml of Remifentanil (R) regimens, as shown in Figure 1.

**Figure 1: Schematic Representation of Procedure Schedule**

Descriptions of the two treatment regimens are as follows:

**Propofol (P) Regimen**

The initial target effect-site concentrations of propofol will be 0.5 µg/ml followed by incremental increases in the target effect-site concentrations of 1.5, 2, 2.5, 3, 4, 6, or 8 µg/ml until MOAA/S scales at values less than 2 is reached. The propofol concentration will be decreased by the same steps until consciousness re-occurs.

**Propofol with Remifentanil (R) regimen**

Where remifentanil is administered with propofol, approximately 2 minutes before starting propofol, to attain an effect-site targeted concentration of remifentanil of 4 ng/ml, remifentanil will be given by a continuous infusion. Approximately within 7 minutes, the infusion rate of Remifentanil may be adjusted to maintain the effect-site concentration of remifentanil of 4 ng/ml throughout the study.

The initial target effect-site concentrations of propofol will be 0.5 µg/ml followed by incremental increases in the target effect-site concentrations of 1.5, 2, 2.5, 3, 4, 6, or 8 µg/ml until MOAA/S scales at values less than 2 is reached. The propofol concentration will be decreased by the same steps until consciousness re-occurs.

The equilibration time for each targeted plateau will be at least 12 minutes. The BIS value will be recorded, and MOAA/S score will be assessed when the patient is awake and at the different targeted concentrations.

## 6 Determination of Sample Size

---

Up to 30 subjects will be enrolled to collect data from approximately 20 subjects and to account for anticipated screen failures and subject dropouts. Based on the dose-response Hill equation (extended logistic regression) with an allowable error of  $\pm 15\%$  for BIS50 and coefficient of variation of 25% at the alpha level of 0.05, the sample size will provide adequate power (>80%) to evaluate the performance of anesthetic agents/regimens.

## 7 Statistical Methods

---

### 7.1 Study Subjects

#### 7.1.1 Disposition of Subjects

Subject disposition will be summarized with frequency tables.

#### 7.1.2 Clinical Investigation Plan (CIP) Deviations

A study deviation is defined as an event when the investigator or site personnel did not conduct the study according to the protocol or the clinical trial agreement.

Study deviations must be reported, regardless of whether medically justifiable, pre-approved by the study leader, or taken to protect the subject in an emergency. All deviations will be summarized descriptively.

#### 7.1.3 Analysis Sets

All evaluable data analysis: Subjects who signed informed consent, meet all inclusion/exclusion criteria and have valid study data. The primary effectiveness analysis will be based on all evaluable data from this study.

Per-Protocol analysis: A per-protocol analysis will be performed based on all subjects who are compliant with the study protocol, provide valid informed consent, do not experience any major protocol deviations, and complete the study procedure.

Subjects who discontinue participation prematurely will be included in the analysis of results. Subjects who withdraw from the study prior to completing both regimens will be replaced by a new volunteer.

## 7.2 General Methodology

[figure not shown]
All statistical analyses will be performed using Statistical Analysis System (SAS) for Windows (version 9.2 or higher, SAS Institute Inc. Cary, NC) or other widely accepted statistical or graphical software. In general, data for all study subjects will be presented. Individual data will be presented in subject listings.

Descriptive statistics will be used to present the data and to summarize study outcomes. Discrete variables will be presented using frequency distributions and cross tabulations. Continuous variables will be summarized by presenting the number of observations (N), mean, standard deviation, median, minimum, and maximum values.

For safety assessments, adverse events will be summarized using frequency counts and percentages. Any unexpected adverse events will be reported and discussed.

### 7.2.1 BIS Value Analysis

The volunteers will receive two regimens of anesthesia with different drug combinations, with at least a 1-week washout period between regimens. Once the pre-procedure part completed, the subject will be sequentially assigned to start with either Propofol (P) or Propofol with 4 ng/ml of Remifentanyl (R) regimens, as shown in Figure 1. The volunteers will have BIS Monitoring System, the 4 Channel BISx, and BIS bilateral sensor placed on their forehead during these regimens to study the effects of these drugs on the brain. Each volunteer will be given a dose range of sequences of the target drug to achieve targeted drug concentration

The modified Observer's Assessment of Alertness/Sedation (MOAA/S) scale will be used to perform sedation/ loss of consciousness assessment. Any subject who responds to any verbal command with MOAA/S assessment score of 3, 4, and 5 will be considered as responsive. Subjects with MOAA/S assessment score of 0, 1, and 2 will be considered unresponsive.

The BIS is a variable derived from the electroencephalograph (EEG) that has been reported to have the ability to measure the hypnotic component of the anesthetic state. It is a dimensionless number from 0 to 100, and decreasing values indicate more sedation and hypnosis.

The MOAA/S scales and BIS value will be assessed and recorded when the subject is awake and at different drug concentrations. The relationship between anesthetic agent concentrations and BIS responses will be modeled using the Sigmoid  $E_{max}$  model (Hill equation). The model is shown as follows:

$$E = E_0 + \frac{E_{max} \times C^\gamma}{(C_{50})^\gamma + C^\gamma}$$

In this model, the treatment effect ( $E$ ) is related to the measured concentration ( $C$ ) of an anesthetic agent according to a nonlinear function with  $\gamma$  defining the steepness of the concentration effect relationship.  $E_0$  is the baseline measurement of the responsive endpoint when no drug is present and  $E_{max}$  is the maximum drug effect. The target parameter  $C_{50}$  is the concentration at which 50% subjects are unresponsive.

With zero effect when no drug is applied, the above model can be expressed as a fraction of maximum drug effect, that is,

$$P = \frac{1}{1 + (C_{50}/C)^\gamma}$$

where  $P$  is the fraction  $E/E_{max}$ . This is an extended logistic model with  $P$  as the probability of “unresponsive”. The model will be fit to the data of BIS values along with drug concentrations. The BIS values will be assessed at the different targeted-controlled drug concentrations, or infusion rates, or ET concentration at which 50% (BIS50) and 95% (BIS95) of subjects are unresponsive. The systematic variance between groups will be evaluated. The Prediction Probability score ( $P_k$ ) for correctly predicting if the subject was responsive or unresponsive will be assessed using the Smith Method.

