Study Design	This is a single-center, prospective, non-randomized, cross-over study to collect data to evaluate the relationship between BIS™ and anesthetic regimens. The subjects will receive two regimens of anesthesia with different drug combinations, with at least a 1-week washout period between regimens. Subjects will be sequentially assigned to start with either Propofol (P) or Propofol with 4 ng/ml of Remifentanyl (R) regimens with the BIS™ bilateral sensor placed on the subject's forehead. The Modified Observer's Assessment of Alertness/Sedation (MOAA/S) scale will be used to measure the level of alertness in sedated subjects, with Tetanic Electrical Stimulation (TES) being used once the patient is unresponsive to tactile stimuli (e.g., MOAA/S < 2). The loss of tactile stimulus response will be defined according to the MOAA/S score value <2.

Medtronic Controlled Information

Clinical Investigation Plan

[figure not shown]
SONORA

MDT19049SONORA

Version 5.0

Page 11 of 75

Medtronic

	
TES will then be initiated once the subject reaches an MOAA/S <2, with a one-time stimulation of 50mA, 50 Hz delivered for 5 seconds. The subject's response will be recorded along with the BIS™ value prior to stimulation, at the time of stimulation and 2 minutes following stimulation. The data will be used to gauge the influence of stimulation on the subject's level of sedation, pre-TES and post-TES.
 
Sample Size	
To collect 20 complete data sets, up to 30 subjects will be enrolled to account for anticipated screen failures and subject dropouts. Based on the dose-response Hill equation with an allowable error of $\pm 15\%$ for BIS₅₀ and coefficient of variation of 25% at the alpha level of 0.05, the sample size will provide sufficient power (>80%) to evaluate the performance of anesthetic agents/ regimens.

Duration	
The study duration is expected to be up to approximately 4 months. The expected duration of each subject will be approximately (~) 10 hours. The Enrollment Visit should take approximately 2 hours to complete, and each Study Visit will be approximately 4 hours per subject. Each subject will be contacted by phone within 48 hours of the study participation.

Planned number of sites	
1 site in the US

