Statistics	
Data will be analyzed by Medtronic or its designee. Any changes in statistical methods will be detailed in the Clinical Study Report.
 
Standard demographic information and baseline characteristics will be summarized using descriptive statistics. For safety assessments, adverse events (AEs) will be summarized using frequency counts and percentages. Descriptive statistics will be provided by severity and relationship as needed.
 
The primary effectiveness analysis will be based on all evaluable data collected from the left side of the brain to reflect the typical operation of the device from this study. The BIS™ index value collected from the right side of the brain will be used for research.
 
Subjects who discontinue participation prematurely will be included in the analysis of results. Subjects who withdraw from the study prior to completing both regimens will be replaced by a new subject.
 
The data will be analyzed for each regimen to evaluate the dose-response relationship of the anesthetic agent concentration and BIS™ values.
 
Any subject who responds to any verbal command with MOAA/S assessment score of 2, 3, 4, and 5 will be considered as responsive. Subjects with MOAA/S assessment scores <2 will be considered unresponsive.
 
The value of BIS™ will be assessed at the different targeted-controlled drug concentrations or infusion rates. The logistic regression (simplified E_{max} model) will be used to analyze the relationship between the BIS™ index and loss of responsiveness through the probability of response curves. The values of BIS™, at which 50% (BIS₅₀) and 95% (BIS₉₅) of subjects are unresponsive, and their 95% confidential intervals will be derived. The systematic variance between groups will be evaluated. The Prediction Probability score (P_k) for correctly predicting if the subject was responsive or unresponsive will be assessed.

-------------------	--

4. Introduction

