14.3. Statistical Methods

Standard demographic information and baseline characteristics will be summarized using descriptive statistics. For safety assessments, adverse events (AEs) will be summarized using frequency counts and percentages. Descriptive statistics will be provided by severity and relationship as needed.

Any subject who responds to any verbal command with MOAA/S assessment score of 2, 3, 4, and 5 will be considered as responsive. Subjects with MOAA/S assessment scores of <2 will be considered unresponsive. Tetanic Electrical Stimulation (TES) will be employed with an MOAA/S assessment score of <2.

The BIS^{TM} index value collected from the left side of the brain will be used for primary analysis to reflect the typical operation of the device from this study. The BIS^{TM} index value collected from the right side of the brain will be used for internal research purposes.

The value of BIS^{TM} will be assessed at the different targeted-controlled drug concentrations or infusion rates. The logistic model (simplified Sigmoid E_{max} model) will be used to analyze the relationship between the BIS^{TM} index and loss of responsiveness through the probability of response curves. The values of BIS^{TM} , at which 50% (BIS_{50}) and 95% (BIS_{95}) of subjects are unresponsive, and their 95% confidential intervals will

be derived. The systematic variance between groups will be evaluated. The Prediction Probability score (P_k) for correctly predicting if the subject was responsive or unresponsive will be assessed.

15. Ethics

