Appendix A – Modified Observer’s Assessment of Alertness/Sedation scale

The Modified Observer Assessment of Alertness/Sedation (MOAA/S) Scale [51]	
Response	Score
Responds readily to name spoken in normal tone	5
Responds lethargically to name spoken in normal tone	4
Responds only after name is called loudly, repeatedly, or both	3
Responds only after mild to moderate prodding or shaking	2
Responds only after painful trapezius squeeze	1
Does not respond to painful trapezius squeeze	0

Clinical Investigation Plan

SONORA

MDT19049SONORA

Version 5.0

Page 74 of 75

[Redacted text block]

[Redacted text block]

- | [Redacted list item]
- | [Redacted list item]
- | [Redacted list item]
- | [Redacted list item]
- | [Redacted list item]

[Redacted text block]

19. Version History

Version	Summary of Changes	Author(s)/Title
1.0	Not Applicable, New Document	[name]./ Sr. Clinical Program Manager
2.0	Administrative Change Only 9.5.2.3	[name]./ Sr. Clinical Program Manager
3.0	Administrative Change Date Alignment pg.1 and pg. 2 / Table 2. Updated CBC to visit 1	[name]./ Sr. Clinical Program Manager
4.0	Revision change from CIP template vs A to vs B Addition of TES assessment Simplification of study procedures and assessments from paragraph form to bullet points Clarification of Study Products vs equipment Separate section of study site requirements for clarity Separate section of Adverse Events and Device Deficiencies for clarity Reformatting of tables for clarity Updated Sponsor contact information Addition of Subject Death reporting requirements for clarity Separation of investigator vs sponsor record retention requirements Addition of tables clarifying reporting requirements	[name], BS, CCRC Sr. Clinical Research Specialist
5.0	Change of procedure to increase anesthesia until a BIST™ value of 30 is reach or per Investigator's discretion Formatting changes Clarification of Statistical Plan	[name], BS CCRC Sr. Clinical Research Specialist

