### 3 Introduction

---

Electroencephalography is an electrophysiological monitoring method to record electrical activity of the brain. An electroencephalogram (EEG) is a test or record of brain activity produced by electroencephalography. Changes in the EEGs are produced by anesthetic agents administered to patients. Bispectral Index (BIS) technology monitoring uses processed EEG signals to measure sedation depth based on level of consciousness (LOC) signals and allows anesthesia providers to titrate general anesthesia to achieve the desired LOC on the brain. BIS technology consists of a sensor, a digital signal converter, and a monitor. The sensor is placed on the patient's forehead to pick up the electrical signals from the frontal cortex and transfer them to the digital signal converter.

This is a single-center, prospective, non-randomized, cross-over study that aims at collecting data for the evaluation of the relationship between BIS and levels of sedation.

The volunteers will receive two regimens of anesthesia with different drug combinations, with at least a 1-week washout period between regimens. Volunteers will be sequentially assigned to start with either Propofol (P) or Propofol with 4 ng/ml of Remifentanyl (R) regimens while BIS bilateral sensor placed on the subject's forehead. The Modified Observer's Assessment of Alertness/Sedation (MOAA/S) scale will be used to measure the level of alertness in sedated subjects.

All enrolled subjects may be invited to participate in the product development sub-part of the study. The purpose of non-contact monitoring Sub-Study (NCM Sub-Study) is to collect data for further exploration of a non-contact physiological monitoring system based on depth-sensing camera technology.

The study duration is expected to be up to approximately 4 months. The expected duration of each subject will be approximately (~) 10 hours. The Enrollment Visit should take approximately 2 hours to complete, and each Study Visit will be approximately 4 hours per subject. Each subject will be contacted by phone within 48 hours of the study participation.

This document provides a detailed description of the statistical methods and procedures to be implemented during the analysis of the study.

This statistical analysis plan (SAP) is based on the CIP Version 1 dated on 12-DEC-2019.

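### The SAP counts MOAA/S 2 as unresponsive and the protocol counts it as responsive, so BIS50, BIS95 and Pk each have two definitions

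*SAP*

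**What the plan says.** **SAP 7.2.1 (BIS Value Analysis).** "Any subject who responds to any verbal command with MOAA/S assessment score of 3, 4, and 5 will be considered as responsive", followed by "Subjects with MOAA/S assessment score of 0, 1, and 2 will be considered unresponsive".

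**Protocol 14.3 (Statistical Methods).** "Any subject who responds to any verbal command with MOAA/S assessment score of 2, 3, 4, and 5 will be considered as responsive", followed by "Subjects with MOAA/S assessment scores of <2 will be considered unresponsive". The Statistics row of the synopsis repeats the rule: "Subjects with MOAA/S assessment scores <2 will be considered unresponsive". The Study Design row of the synopsis adds: "The loss of tactile stimulus response will be defined according to the MOAA/S score value <2".

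**The scale.** Protocol Appendix A defines score 2 as "Responds only after mild to moderate prodding or shaking". Score 3 is a response to a loudly or repeatedly called name, and score 1 is a response only to a painful trapezius squeeze.

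**Which text governs.** Protocol section 14 says the analyses follow the SAP. SAP section 3 says: "This statistical analysis plan (SAP) is based on the CIP Version 1 dated on 12-DEC-2019". The SAP's version history shows only Version 1.0, and the protocol is Version 5.0. Neither document says which prevails if they differ.

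**The concern.** The primary objective is the BIS value at which half of subjects are unresponsive. BIS95 and Pk use the same binary outcome. If the outcome is split at a different score in each document, each of these has two definitions.

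The two splits also measure different things. Splitting between 3 and 2 locates loss of response to voice. Splitting between 2 and 1 locates loss of response to touch. An analyst who follows the SAP, as the protocol instructs, would report results for an outcome that the current protocol contradicts. If the conflict is left until the data are in, the cut could be chosen after both answers have been seen.

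**Working it through.** **1. The two classifications side by side**

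| MOAA/S | Stimulus needed (Appendix A) | SAP 7.2.1 | Protocol 14.3 and synopsis |
|---|---|---|---|
| 5, 4, 3 | voice | responsive | responsive |
| 2 | prodding or shaking | **unresponsive** | **responsive** |
| 1 | painful squeeze | unresponsive | unresponsive |
| 0 | none effective | unresponsive | unresponsive |

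The unresponsive sets are {0, 1, 2} and {0, 1}, and the difference is {2}. Every assessment scored 2, on the way up or down the concentration steps, changes class with the document followed.

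**2. Direction.** The SAP set contains the protocol set. If score-2 readings lie at intermediate BIS values, the SAP cut gives a higher BIS50 and a higher BIS95. The effect on Pk was not quantified.

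**3. The plan's own figure.** Protocol 14.1 gives about 20 subjects, ±15% error, CV 25%, alpha 0.05 and power above 80%. Treating BIS50 as a one-sample mean:

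- error / (CV/√n) = 0.15 / (0.25/√20) = 2.683
- one-sided: Φ(2.683 − 1.645) = 85.0%
- two-sided: Φ(2.683 − 1.960) = 76.5%

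The stated power is reproduced with a one-sided alpha; sidedness is not stated. The MOAA/S cut is not an input here, so the conflict leaves the sample size unchanged.

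**4. Size, on assumed inputs.** The documents give no BIS distance between the 3-to-2 and 2-to-1 transitions, so gaps of 3, 5, 10 and 15 points were assumed. The model was as follows (all values not in the protocol are assumptions):

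- 200 simulated trials of 20 subjects, stepping from awake through the protocol's propofol targets and back.
- BIS = 95 − 65·C^2.5/(C50^2.5 + C^2.5) plus noise of SD 4, with C50 lognormal (median 3 µg/ml, log-SD 0.25). Readings below 30 were dropped.
- Score falls below 2 when BIS is under 60, with between-subject SD 6 and within-subject SD 4. Score falls to 2 or less when BIS is under 60 + gap.
- Pooled logistic regression, logit P(unresponsive) = a + b·BIS, so BIS50 = −a/b and BIS95 = (ln 19 − a)/b.

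| Assumed gap | BIS50, protocol cut | BIS50, SAP cut | Change | BIS95, protocol cut | BIS95, SAP cut | Readings scored 2 |
|---|---|---|---|---|---|---|
| 3 | 60.0 | 63.0 | +5.0% | 48.8 | 51.8 | 3.6% |
| 5 | 60.0 | 64.9 | +8.3% | 48.6 | 53.6 | 6.1% |
| 10 | 59.9 | 69.9 | +16.5% | 48.8 | 58.5 | 12.6% |
| 15 | 60.0 | 74.9 | +24.8% | 48.8 | 63.8 | 19.5% |

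Percentages come from unrounded means. A separate simulation of 3,000 subjects, with BIS starting at 97, gave a BIS50 of 60.5 under the protocol cut and 63.6, 65.7, 70.9 and 75.5 under the SAP cut.

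**5. Scale.** The ±15% error equals 0.15 × 60 = 9.0 points at a BIS50 of 60, or 0.15 × 65 = 9.75 points at 65. A gap of about 10 points would exceed either.

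**The case against.** The contradiction itself cannot be disputed, since both texts are current. The objections concern its reach, its size and the remedy.

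- **Choice of side.** The protocol describes scores 2–5 as answering a verbal command, but score 2 is a response to touch. The SAP uses the same description for 3–5, where it fits the scale. On that sentence the SAP is the coherent document, and the protocol defers to the SAP for analysis. This shows that the protocol wording also needs repair. It does not outweigh the evidence for a cut below 2: the later protocol version, whose history lists a clarification of the statistical plan; the definition of loss of tactile response; the use of the same threshold for tetanic stimulation; and the SAP's own regimen descriptions, which also refer to scores below 2.
- **Size.** Moving a threshold by X moves BIS50 by about X, so the simulation largely restates its input. The ±15% is a sample-size input, not a tolerance for a change of definition. Both points stand: the table is an illustration and the 15% is only a yardstick.
- **Reach.** The SAP's curve of BIS against drug concentration does not use the MOAA/S split. That is correct; the finding concerns BIS50, BIS95 and Pk.
- **Consequence.** No hypothesis or success threshold is attached to BIS50, both splits can be computed from the recorded scores, and changes in method are to be described in the study report. This limits the harm, but reporting a change afterwards does not replace fixing the primary outcome in advance.

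**Conclusion.** The concern holds. The SAP and the current protocol classify MOAA/S 2 in opposite ways, nothing in either document settles the conflict, and BIS50, BIS95 and Pk all depend on it. This is an error in the plan as written and must be corrected.

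The contradiction needs no assumption. Its numerical size does: the shift in BIS50 is roughly the BIS distance between losing response to voice and losing response to touch, which the documents do not give. Over assumed gaps of 3 to 15 points the shift is about 3 to 15 points, or 5% to 25% of a BIS50 of 60. It is systematic, so enrolling more subjects would not reduce it.

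**What to change.** Re-issue the SAP against CIP v5.0. In SAP 7.2.1, define responsive as MOAA/S 2–5 and unresponsive as 0–1, in line with protocol 14.3. Report the 0–2 split only as a labelled sensitivity analysis. If the sponsor in fact intends loss of response to voice, both documents must say so, with a reason, before the data are analysed.

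In the protocol synopsis and 14.3, remove the reference to verbal command wherever the responsive group includes score 2. Use one wording for score 2 in both appendices; the SAP's version omits the moderate level of prodding.

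In the same revision, carry the protocol's rule on using left-side BIS for the primary analysis into the SAP. The two descriptions of how far propofol is escalated also differ (MOAA/S below 2 in the SAP, a BIS floor of 30 in the protocol) and must be reconciled; this review takes no position on which is right.

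The cost is a SAP revision and a small protocol wording change, to be made before database lock. No new data are needed, because the MOAA/S score is recorded at each step.

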### Secondary Objective:

To determine BIS95 (BIS value at which 95% of subjects will be unresponsive at given drug concentrations) and other dose-response parameters.

The relationship between anesthetic agent concentrations and BIS responses will be modeled using the Sigmoid model (extended logistic model) as discussed previously.

The dose-response relationship by drug concentration will be presented. The estimated BIS values along with 95% confidence intervals will be provided for propofol with or without remifentanyl regimens.

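### SAP 7.2.1 and 7.9 give no estimator for BIS50 or BIS95: their equations run on drug concentration, while the protocol models loss of responsiveness on BIS

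*SAP*

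**What the plan says.** Protocol 14.3 (and the Statistics row of the Synopsis) applies a logistic model, described as a simplified sigmoid Emax model, to the relation between the BIS "index and loss of responsiveness through the probability of response curves". BIS50, BIS95 and their 95% confidence intervals come from that curve. Protocol 14 sends the statistical analyses to the SAP.

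SAP 7.2.1 writes two equations:

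- E = E0 + Emax·C^γ / (C50^γ + C^γ), introduced as a model of BIS on drug concentration;
- P = 1 / (1 + (C50/C)^γ), where P is defined as E/Emax and then also as the probability of being unresponsive.

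The target parameter C50 "is the concentration at which 50% subjects are unresponsive". The fitting instruction is "The model will be fit to the data of BIS values along with drug concentrations". BIS50 and BIS95 appear only in the next sentence: "The BIS values will be assessed at the different targeted-controlled drug concentrations, or infusion rates, or ET concentration at which 50" or 95 per cent of subjects are unresponsive.

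SAP 7.9, which covers both objectives, says "The relationship between anesthetic agent concentrations and BIS responses will be modeled using the Sigmoid model (extended logistic model) as discussed previously". It promises estimated BIS values with 95% confidence intervals and gives neither a formula nor an interval method.

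The binary outcome also differs. Protocol 14.3 states "Subjects with MOAA/S assessment scores of <2 will be considered unresponsive", with a score of 2 counted as responsive. SAP 7.2.1 states "Subjects with MOAA/S assessment score of 0, 1, and 2 will be considered unresponsive". SAP 3 explains the likely origin: "This statistical analysis plan (SAP) is based on the CIP Version 1 dated on 12-DEC-2019". The current protocol is Version 5.0.

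**The concern.** The primary and secondary objectives are values on the BIS scale, and the document that governs the analysis has no equation with BIS as the predictor of responsiveness. This is more than missing detail, because the SAP states a different model. It equates a graded fraction of the BIS effect with a probability of unresponsiveness, and it does not name MOAA/S as the fitted outcome.

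Two competent programmers could therefore report different results from the same data:

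- **Reading A (as literally written):** fit the Hill curve to BIS against concentration and take the 50% point of E/Emax.
- **Reading B (generous):** fit responsiveness against concentration, then read BIS off at C50 and C95, as the sentence on BIS50 and BIS95 implies.

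Neither is the protocol's curve. Reading A does not measure where subjects stop responding. Reading B targets a different BIS95 and can require extrapolation beyond the highest planned propofol target of 8 µg/ml.

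**Working it through.** **1. The plan's own figure.** The only figures attached to BIS50 are in the sample-size statement: ±15% allowable error, CV 25%, alpha 0.05, about 20 subjects, power above 80%. As a one-sample mean, power = Φ(0.15·√20/0.25 − z), and 0.15·√20/0.25 = 2.683. One-sided: Φ(2.683 − 1.645) = 85.0%. Two-sided: Φ(2.683 − 1.960) = 76.5%. The claim is reproduced one-sided. It says nothing about which model yields BIS50, but ±15% gives a yardstick: 7.5, 9.75 and 11.25 points at a BIS50 of 50, 65 and 75.

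**2. What each route solves for.**

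| Route | Outcome | Predictor | 50% point | 95% point |
|---|---|---|---|---|
| Protocol 14.3, as logit P = a + b·BIS | unresponsive | BIS | BIS50 = −a/b | BIS95 = (ln 19 − a)/b |
| SAP second equation | P | concentration | C50 | C50·19^(1/γ) |
| SAP first equation | BIS | concentration | half the BIS effect | not defined |

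The SAP rows give concentrations or a fraction of effect. BIS is never the argument of P.

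**3. Reading A, algebra.** Setting E/Emax = 0.5 in the first equation gives BIS = E0 + Emax/2, with Emax negative. MOAA/S does not enter. The step to P also assumes zero effect without drug, whereas Protocol 4.1.2 puts awake BIS at 100.

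**4. Reading B, one worked case.** Assume a true logistic on BIS with BIS50 65 and slope 5, awake BIS 95 falling by up to 75 along a Hill curve with exponent 2, median EC50 3 µg/ml and BIS noise SD 6. The true BIS95 is 65 − 5·ln 19 = 65 − 5·2.944 = 50.3. With between-subject log-SD of EC50 at 0.2, the logistic on BIS gave 50.2 and BIS at C95 gave 42.6. At log-SD 0.4 they were 50.4 and 37.3. The reason is that C95 must be high enough for insensitive subjects, so the population curve read there lies below the BIS at which 95% stop responding. Across eight such settings BIS50 agreed to about 1 point and BIS95 was 6 to 14 points lower.

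**5. Wider grid.** The documents supply the propofol plateaus, the BIS limit of 30 and n = 20. The other inputs are assumptions: awake BIS 95; BIS floor 15 or 30; γ 2 or 3; median EC50 2.5 or 3.5 µg/ml; log-SD 0.2 or 0.4; BIS noise SD 5; subject thresholds with CV 10% or 20% around 50, 65 or 75, kept within 20 to 88. That is 2·2·2·2·2·3 = 96 sets of 3,000 subjects, stepping up until expected BIS would fall below 30 and then down until responsive. The logistic on BIS recovered the generated median threshold within 1.8 points in every set.

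- *Reading A:* midpoint 59.0 to 68.7 in all sets. Offset +11 to +19 at an assumed BIS50 of 50 (always beyond 7.5), −5 to +4 at 65, and −16 to −4 at 75 (in part beyond 11.25).
- *Reading B, BIS50:* within 2.1 points of the logistic-on-BIS value in all 96 sets.
- *Reading B, BIS95:* differs by a median of 8.9 points (CV 10%) or 5.7 points (CV 20%), range −17.7 to +10.6, usually lower. C95 exceeds 8 µg/ml in 27 of 96 sets (28%).
- *Sensitivity:* if response follows true rather than recorded BIS, the median BIS95 gap is 4.4 to 4.7 points. At threshold CV 25% the median is −3.5 points (range −10.7 to +11.0), with C95 above 8 µg/ml in 20 of 48 sets.

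**6. Functional form and intervals under the protocol's route.** A logistic in ln(BIS), equivalent to P = 1/(1+(BIS/BIS50)^γ), moves BIS95 by 0.3 to 2.9 points. With 20 subjects (about 190 to 240 plateau rows; 700 simulated trials at each of four settings), treating rows as independent gave 66–78% coverage for BIS50 and 74–85% for BIS95, against a nominal 95%. Cluster-robust variance with t(19) gave 94–96% and 90–92%.

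**The case against.** The strongest reply is that Protocol 14.3 already states the right model, so a programmer holding both documents has it and the SAP is merely out of date. That explains the origin, but Protocol 14 gives the SAP control and the SAP states a conflicting model. The protocol does not settle the conflict by itself.

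Other points stand in part:

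- Nowhere does the SAP define BIS50 as the BIS midpoint, and neighbouring sentences speak of the concentration at which subjects are unresponsive. Reading A follows from the fitting instruction plus P = E/Emax, but the largest offsets come only from it and should carry less weight.
- The objectives in both documents refer to given drug concentrations, which lends Reading B support. That is a real ambiguity, and it sits in the protocol as well.
- Under Reading B the primary estimate barely moves, and no test or success threshold for BIS50 is stated. The numerical harm under that reading falls on BIS95.
- The BIS95 gap depends on the inputs and shrinks with a wider threshold spread. Taking the documents' 25% as that spread is itself an assumption, and the extrapolation problem does not shrink with it.
- The protocol's simplified sigmoid Emax wording could mean the power form instead of the linear logistic.
- Poor coverage from ignoring repeated plateaus would arise under the protocol's model too. It bears on how to write the correction and is not evidence for this defect.

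**Conclusion.** The concern holds and should be corrected before the analysis. On the text alone, the SAP has no estimator of the protocol's BIS50 or BIS95, gives P two incompatible meanings, and uses a different MOAA/S cut-off from the protocol. The simulations only gauge size. Reading A does not track loss of responsiveness at all. Reading B leaves BIS50 within about 2 points of the logistic-on-BIS value but typically puts BIS95 several points lower, and can need concentrations above 8 µg/ml. Those sizes, and for BIS95 the direction, rest on the assumed BIS curve, between-subject spread and response mechanism. The textual finding does not.

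**What to change.** In SAP 7.2.1 and 7.9:

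1. Make the primary model, per regimen, logit P(unresponsive) = a + b·BIS, using left-side BIS recorded just before each MOAA/S assessment. State BIS50 = −a/b and BIS95 = (ln 19 − a)/b. Prespecify this one form, since the power form gives a different BIS95.
2. Name a 95% interval method that respects repeated plateaus within subject: a subject-level bootstrap, or cluster-robust variance with a t reference. The latter fell a little short for BIS95 (90–92%) and bootstrap coverage was not examined, so check the chosen method by simulation before database lock.
3. Reconcile the MOAA/S cut-off and state one rule in both documents.
4. Keep the Hill model of BIS on concentration (free E0, negative Emax) as a separate supportive analysis for the dose-response aim in the protocol Synopsis. Label its C50 as the concentration of half-maximal BIS effect, and delete the statement that its P is the probability of being unresponsive.
5. Remove or explain the reference to given drug concentrations in the objectives of both documents.
6. Re-base the SAP on protocol Version 5.0.

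The cost is rewording and a simpler programme. BIS before MOAA/S, the MOAA/S score and the target concentrations are already collected.
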